## 4.6.15 : Neurocognitive testing

Neurocognitive testing will be conducted before and after CPET. The TOVA, HVLT-R, BVMT-R, and the B-Test and/or Dot Test will be measured pre-exercise and may be measured up to four times following CPET.

#### 4.6.16 : Holter monitoring

Heart rate variability will be assessed using standardized Clinical Center EKG/Holter Monitor data, which will be collected per NIH Cardiology standard routines. The EKG monitoring will last less than 24 hours and will be done pre-exercise and post-exercise.

## 4.6.17 : fMRI

fMRI will be completed during the exercise stress visit and will occur on two separate days, once before and once after the exercise challenge. The following imaging paradigm will be utilized: The subject will lie in the scanner operating a dynamometer to measure the force generated by the muscles of the distal upper limb in a first phase of the scan, and a button box for answering a cognitive test in the second phase of the scan. A structured set of imaging tasks are planned. An optional MRI-compatible electroencephalogram cap may be installed on subject's head before installing the subject in the MRI scanner in order to monitor the cortical activity during fMRI scanning and to allow the measurement of the cortico-muscular coupling during the muscular and cognitive fatiguing exercises. This may add about 30 min to the setup time.

Each scanning session will begin with a localizing image, an anatomical scan, and resting-state BOLD acquisition (20 minutes).

A test of cognitive fatigue will be performed within the MRI environment before the muscular fatigue test. In this study, there will be a sequence of two-choice reaction times. The correct choice will be based on a simple cognitive operation and the difficulty of the operation will not change over the series. Cognitive fatigue will be deemed present if the reaction time increases over the sequence. The test will continue for 10 minutes. fMRI will be done for 10 minutes, and the task analyzed as an event related design. The time between reaction time trials will be jittered, so that the MR signal can be extracted. The behavioral data and the MR data will be related parametrically. Another resting BOLD acquisition will be performed after the cognitive task. Even if no significant learning is expected related to the task, the subjects will get some training on the task prior to the MRI study so the novelty and/or any amount of learning will be further minimized. Subjective appraisals of cognitive fatigue will be measured at intervals during the cognitive fatigue task (20 minutes).

A test of muscular fatigue will be performed afterwards within the MRI environment. The last resting BOLD acquisition for the prior test can be considered the baseline for this test. We will determine maximum voluntary contraction (MVC) of the forearm muscles, expressed in newtons, from the best of three brief presses on the dynamometer. After a resting period, the subject will perform repeated 30-second blocks of isometric muscle contractions at half MVC until fatigued, which is defined as the inability to maintain at least 40% MVC force for more than 3sec. The subject and the investigators will have visual feedback from a computer to monitor force generation. The approximate interval between successive exercise periods will be 30 seconds. The period after the last exercise will be the recovery period, during which resting BOLD will be acquired. Acquisition time will be the same length for all subjects, with fatigued subjects simply stopping doing the task for the block. Subjective appraisals of muscular fatigue will be measured at intervals during the muscular fatigue task (30 minutes).

If MPRAGE, DWI, and T2w images have not been previously collected on a study dedicated MRI machine at the NMR Center, they will be obtained at this time. If an MRI-

compatible cap was installed and further DWI scans are necessary, the cap will be removed prior to the DWI scan. (25 minutes).

The fMRI procedures will all be completed on the same scanner at the NMR center and should take approximately 90-120 minutes to complete. All women of childbearing potential will have a urine pregnancy test performed no more than 24 hours before each fMRI session.

## 4.6.18 : Effort-Expenditure for Rewards Task (EEfRT)

The Effort-Expenditure for Rewards Task is a multi-trial game in which participants are offered a choice between two task difficulty levels for a reward. The task begins with a 1 second fixation cross, followed by a 5s choice period in which the participant is informed of the probability of "winning" if the task is completed successfully. After the participant chooses the task, a one second "ready" screen is displayed. Next, the participant either completes thirty button presses in seven seconds with the dominant index finger if they have chosen the easy task, or one-hundred button presses in 21 seconds using the non-dominant little finger if they have chosen the hard task. Next, the participant receives feedback on whether or not they completed the task successfully. Finally, the participant learns if they have "won", based upon the probability of winning and the successful completion of the task. This process repeats in its entirety for twenty minutes. This task will evaluate the theory of value-based decision making in the pathophysiology of fatigue by looking for associations between MRI brain measurements implicated in reward and measures of fatigue and motivation in our subjects. In the initial validation study, trait anhedonia as measured by well-validated self-report measures significantly predicted an overall reduced likelihood of making a hard-task choice (b = -.015, p<0.005).

Participants are told at the beginning of their task that they will win the dollar amount they receive from two of their trials, chosen at random from the computer program (range of total winnings is \$2.00-\$8.60).

Figure 1. Schematic diagram of a single trial of the modified Effort Expenditure for Rewards Task ('EEfRT'). A. Fixation cross for participant to view, B. 5s choice period in which subjects are presented with information regarding the reward magnitude of the hard task for that trial and probability of receiving any reward for that trial, C. 1s "ready" screen, D. Subjects make rapid button presses to complete the chosen task for 7s (easy task) or 21s (hard task), E. Subjects receive feedback on whether they have completed the task, F. Subjects receive reward feedback as to whether they received a score increase for that trial (adapted from Treadway, 2009).

#### 4.6.19 : Lumbar puncture

All participants will undergo an LP to collect cerebrospinal fluid (CSF) for research. The LP will be done at the Clinical Center at the bedside or in Radiology if done under fluoroscopy. The NIH Radiation Safety Committee guidelines will be followed for participants undergoing LP under fluoroscopy. Analysis of CSF may include (but will not be limited to): opening pressure, cell count, total protein, glucose, PCR for pathogens, cytokine assays, lipid profile, and flow cytometry for phenotyping of immune cells (CD4 and CD8 T cells including central memory, central effector, regulatory and naïve T cell subsets, B cells and monocytes), cytokine/chemokine profile, growth factors, proteome and metabolome, autoantibodies to brain antigens and neurotransmitters. CSF will also be aliquoted and stored for future use. Additionally, specialized laboratory testing such as detection of autoantibodies to novel antigens will be performed as needed. The upper limit of CSF withdrawn will be 24 ml. LP will be performed during post-exercise day 3. (30-60 minutes)

## 4.6.20 : Stool Sample Collection

All stool produced during the 12 hours prior to CPET and for 72 hours after CPET will be collected fresh in a cup and placed in an ice bath or refrigerator immediately. These

samples will be retrieved, processed, and frozen within 24 hours. Stool samples will be used for microbiome and micronutrient profiling.

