Healthy volunteers in the technical development sub-study may also participate in the phenotyping and exercise stress visits. Participation in the technical development substudy will be made available to documented ME/CFS patients that inquire about participation in the protocol and would otherwise be eligible to participate but do not meet study criteria for post-infectious causation or for having symptoms for less than 5 years. ME/CFS patients that participate in the technical development sub-study are excluded from participation in the phenotyping and exercise stress visits but may participate in focus groups.

The phenotyping visit (Visit 1) is designed to clearly define and document the characteristics of the study populations as well as collect biological samples. Eligible participants will undergo a set of research measurements and procedures. The results from the phenotyping visit will enable cross-sectional comparisons between the three study groups.

The exercise stress visit (Visit 2) will occur up to 12 months after the phenotyping visit. The exercise stress visit is designed around an exercise intervention designed to evoke the characteristic post-exercise malaise of PI-ME/CFS. All participants will undergo careful clinical description and a variety of biological measurements before, during, and after peak exercise testing. Qualitative interviews, subjective reporting on questionnaires, physiological measurements, neuroimaging, and biological samples will be serially collected. Only HV and PI-ME/CFS participants will be invited to participate in the exercise stress visit. These measurements will enable cross-sectional comparisons between these two study groups as well as comparisons between pre- and post-exercise state within and between study groups.

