#### 4.5 Phenotyping Visit (Visit 1: Phenotyping)

The phenotyping visit will take place at the NIH Clinical Center up to 12 months before the exercise stress visit and is expected to last 5 days for HV and COVID-19 HV participants and 10 days for PI-ME/CFS participants. Phenotyping may occur on either an outpatient or an inpatient admission basis, depending on convenience. Information collected during the phenotyping visit will be used to determine PI-ME/CFS case status as well as to determine eligibility for the exercise stress visit. All procedures are for research purposes.

Consent will be obtained before any study procedures, including screening procedures, are done. Eligibility criteria will be reviewed during the consent process. An eligibility criteria checklist will be reviewed on Visit 1 completion and documented in the protocol's research records.

CNS IRB Protocol Template (2.5.15)

During the phenotyping visit, clinical information that is collected may impact participant eligibility. All participants in the PI-ME/CFS group will have documentation of being diagnosed with the illness in the community. In this way, PI-ME/CFS participants found not to meet inclusion/exclusion criteria during the phenotyping visit still represents what ME/CFS is in the community. For this reason, PI-ME/CFS participants that are found to have alterative or concomitant diagnoses that would otherwise exclude from study participation may still be invited to complete all of the phenotype visit procedures.

Participants in the HV and COVID-19 HV groups may be found to meet exclusion criteria during Visit 1. Such participants are also permitted to complete Visit 1 procedures, as long as they do not have substantial daily fatigue nor concerns for safety. Samples and data from these participants will be used in the primary analysis. HV and COVID-19 HV participants found to have substantial daily fatigue will have their study participation ended immediately and will not be used in primary analyses. Study participation for HV individuals meeting exclusion criteria will be complete at the end of Visit 1. Study participation for all COVID-19 HV individuals will be complete at the end of Visit 1.

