## 4.5.13 : Nutritional Assessment:

Nutrition staff will either meet in person with the participants during their Visit 1 admission or contact consented participants by telephone prior to the Visit 2 admission. During this meeting, participants will be instructed on food record keeping and educated about the controlled metabolic menu that they will have for Visit 2. Selections will be made for the menus that they prefer to have during Visit 2 and food allergies and intolerances will be assessed. Changes to controlled menus will only be made if possible to accommodate food allergies. COVID-19 HV participants will not receive this assessment.

All participants will fill out an internet-based food frequency questionnaire (Diet History Questionnaire (DHQII), National Cancer Institute, Rockville, MD) which asks them 134 questions regarding their dietary intake over the past year and 8 questions about dietary supplement intake. This questionnaire is completed online and typically takes approximately 45-60 minutes to complete. This may be completed during Visit 1 or Visit 2.

Participants will be asked to provide detailed food records for 7 days prior to their admission during the same week that they are wearing the activity monitor and recording the fatigue diary. These food records will be reviewed by NIH nutrition staff for accuracy using 3-dimensional models and then entered into Nutrition Data Systems for Research (NDSR, University of Minnesota, Minneapolis, MN) to obtain nutrient intake. COVID-19 HV participants will not receive this assessment.

4.5.14 : Saliva Sample Collection: Saliva will be collected using 1-2 salivary swabs taken from the anterior floor of the mouth and near the Stenson's ducts. Samples will be collected from a clean mouth at least two hours after the participant's last meal. It takes about one minute to collect a sample.

4.5.15 : Buccal Swab Sample Collection: Buccal swabs will be collected using a brush rotated against the buccal surface. Buccal swabs will be used for microbiome and micronutrient profiling. (<1 minute)

4.5.16 : Stool sample collection: A fresh stool sample will be collected in sterile cup and frozen immediately. Stool samples will be used for microbiome and micronutrient profiling.

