# 4.6.10 : Metabolic Diet and Nutritional Assessment

All participants will consume a controlled metabolic diet for the entire Exercise Stress Visit. Energy needs for weight maintenance will be estimated using the Mifflin St. Jeor equation with an activity factor of 1.5. The diets will be standardized to have 55% of energy from carbohydrate, 30% of energy from fat and 15% of energy from protein. All food and food ingredients will be weighed to the nearest gram weight in the NIH CC Metabolic Kitchen prior to being served to the participant. Though participants should consume all foods provided to them, any food not eaten will be weighed back and then, if possible, nutrients will be replaced the same day.

Participants whom did not previously complete the Diet History Questionnaire (DHQII) will do so. This questionnaire is completed online and typically takes approximately 45-60 minutes to complete. Also, a structured dietary interview to assess dietary avoidances will be conducted by NIH nutritional staff (see appendix 26.3).

4.6.11 Resting Energy Expenditure Measurements by Ventilated Hood While the metabolic hood is the 'gold standard' for metabolic measurements, the technique requires participants to spend long periods of time enclosed in a small room. As a contingency if a participant is found to be unable to tolerate prolonged time in the metabolic chamber, we will perform indirect calorimetry using the ventilated hood technique. This entails having the participants breathe into a transparent plastic hood placed over the head for up to 40 minutes. Ventilated hood measurements will be timed to occur in the morning after a 12 hour fast.

Hood measurements will be made in all participants prior to performing CPET to establish a baseline measurement. No further ventilated hood measurements will be made if the participant is able to tolerate staying in the metabolic chamber. If a participant is found to be unable to tolerate the metabolic chamber, ventilated hood measurements will be made each morning that the participant would have otherwise been in the metabolic chamber.

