## **11 Outcome Measures:**

The primary purpose of this protocol is to perform exploratory analysis of collected samples for the generation of new hypotheses regarding ME/CFS. The types of analyses to be performed will be wide ranging. Planned areas of focus include:

1. Characterization of the immune system and inflammatory signaling in collected samples at baseline and following maximal exercise exertion.

2. Characterization of the pattern of microbiome in collected samples at baseline and following maximal exercise exertion.

3. Characterization of bioenergetics, autonomic, and metabolic function in collected samples at baseline and following maximal exercise exertion.

4. Characterization of physical and cognitive fatigue using functional magnetic resonance imaging and transcranial magnetic stimulation at baseline and following maximal exercise exertion.

5. Characterization of neurocognition at baseline and following maximal exercise exertion.

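### The 12-hour pre-exercise stool window at Visit 2, with no fallback, may leave a substantial share of participants without a same-visit microbiome baseline

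*Combined protocol and SAP*

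**What the plan says.** Section 11 lists as an outcome area: "Characterization of the pattern of microbiome in collected samples at baseline and following maximal exercise exertion". Section 4.1 promises comparisons of the pre- and post-exercise state within and between the PI-ME/CFS and healthy volunteer groups. Section 12.1 plans repeated measures ANOVA and an analysis of change from before to after exercise.

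Two collections supply the stool:

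- **Visit 2 (Section 4.6.20).** "All stool produced during the 12 hours prior to CPET and for 72 hours after CPET will be collected fresh in a cup". The stool is chilled and then "samples will be retrieved, processed, and frozen within 24 hours". Its purpose is stated: "Stool samples will be used for microbiome and micronutrient profiling".
- **Visit 1 (Section 4.5.16).** "A fresh stool sample will be collected in sterile cup and frozen immediately". On the interval between visits, Section 4.1 says: "The exercise stress visit (Visit 2) will occur up to 12 months after the phenotyping visit".

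Section 4.6 describes Visit 2 as an inpatient stay of about 5 to 10 days and defines the Pre-Exercise period as the days before the peak exercise test (CPET). The exercise stress visit table in Section 25.1 marks stool collection under Pre-Exercise, Exercise Day 0 and Post-Exercise Days 1-4, with no hour limit. On diet, Section 4.6.10 says: "All participants will consume a controlled metabolic diet for the entire Exercise Stress Visit".

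The plan does not say which stool is the microbiome baseline, what happens if none is passed in the 12 hours, or how Section 12 treats a missing pre-exercise value.

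**The concern.** A within-person change needs a stool from before and a stool from after exercise. The post-exercise window is six times the pre-exercise window (72 h against 12 h), so the baseline is the limiting half of the pair. A person with about one movement a day can easily pass nothing in a given half-day.

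Two things are at stake. The first is precision: the change is estimated in fewer than the target of 20 completers per group. The second is selection: having a pair depends on bowel frequency and timing. If bowel habit differs between PI-ME/CFS and healthy volunteers, the two sets of complete pairs are selected differently, and the group comparison of change could be biased.

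The Visit 1 sample does not match the Visit 2 post-exercise samples. It may be up to 12 months older, it precedes the controlled diet and the medication wash-out planned for Visit 2, and it is frozen at once rather than chilled and frozen within 24 hours. A change measured from it mixes exercise with time, diet, medication and handling.

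**Working it through.** The plan states no expected stool yield, number of pairs or microbiome power, so there is no figure to reproduce. What follows is a sensitivity calculation.

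**Inputs from the documents:** 12 h before and 72 h after CPET (4.6.20); target of 20 completers per group (3.1); significance level 0.05 (12.1), taken as two-sided.

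**Assumed input:** a bowel-movement rate of *r* per day, varied from 0.5 to 3.

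**Formulas**
- Random (Poisson) timing: P(no stool in *t* days) = exp(−*rt*). P(pair) = [1 − exp(−*rt*)] × [1 − exp(−3*r*)], with *t* = 0.5 for the 12 h window.
- Evenly spaced movements with CPET at a random point in the cycle: P(pre-exercise stool in 12 h) = min(1, 0.5*r*).

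**Worked case, r = 1, random timing**
- No stool in 12 h: exp(−0.5) = 0.607.
- Stool within 72 h after: 1 − exp(−3) = 0.950.
- Pairs of 20 with 12 h: 20 × 0.393 × 0.950 = 7.5.
- With 24 h: 20 × 0.632 × 0.950 = 12.0.
- With 48 h: 20 × 0.865 × 0.950 = 16.4.
- Ratio of standard errors of the mean change, 12 h against 48 h: √(16.4/7.5) = 1.48.

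| Assumed rate | No stool in 12 h, random | No stool in 12 h, even | Pairs of 20, random: 12 h | 24 h | 48 h |
|---|---|---|---|---|---|
| 0.5/day | 78% | 75% | 3.4 | 6.1 | 9.8 |
| 1/day | 61% | 50% | 7.5 | 12.0 | 16.4 |
| 2/day | 37% | 0% | 12.6 | 17.3 | 19.6 |
| 3/day | 22% | 0% | 15.5 | 19.0 | 19.9 |

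**When are more than half of the pairs lost?** Only below about 1.4/day with random timing (at 1.39/day P(pair) = 0.493), or below 1/day with even spacing.

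**Clock time.** For a once-daily habit, if 20%, 50%, 80% or 95% of movements fall inside the 12 h window, then 4, 10, 16 or 19 of 20 pairs are kept. The documents do not fix the hour of CPET.

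**Effect on power.** For a paired test in one group and an assumed standardised change of 0.66, power is 80% with 20 pairs, 69% with 16, 55% with 12 and 37% with 8.

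**Room before CPET.** A 5-day admission with 72 h of follow-up after CPET leaves about 5 − 3 = 2 days before it. The 48 h column is therefore roughly the most that the shortest stay could give.

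**The case against.** The strongest reply is that the size of the problem is not in the documents. A reader might infer that the outcome loses most of its pairs. That holds only at low assumed rates, and daily rhythm could keep nearly all pairs if the window covers the usual time of movement. Section 4.6.11 places a fasting morning measurement before CPET; if CPET followed on the same day, the window would take in part of the night and the morning. This part of the reply stands.

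A reader might also infer that affected participants have no pre-exercise sample at all. That is wrong: every participant is due to give a stool at Visit 1, and Section 11 does not say that the baseline must come from Visit 2. What is missing is a same-visit, like-for-like baseline.

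Third, one might conclude that the diet change cannot be separated from exercise. Both groups at Visit 2 eat the controlled diet and undergo CPET, so a diet effect common to both cancels in the between-group comparison of change. It remains in the within-group change, and a diet effect that differs by group does not cancel.

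Fourth, Section 4.6.20 does not say that earlier stool is discarded, and the Section 25.1 table can be read as wider. That is a reason to reconcile the two, since staff following 4.6.20 would have no instruction to keep earlier stool.

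Finally, the study is exploratory, sized by convenience (12.2) and not powered on the microbiome, and no document shows that bowel habit differs by group. This limits the consequence. It does not supply a baseline that was never collected.

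**Conclusion.** The point holds in a conditional form. The wording is certain: 12 hours before against 72 hours after, no fallback, no named baseline, no rule for a missing pre-exercise value, and a schedule table that reads more widely than the text. The conclusion is that a substantial share of participants may lack a same-visit pre-exercise stool.

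The size rests on an assumed bowel-movement rate and an unstated CPET time. At one movement a day, half (even spacing) to 61% (random timing) would lack the sample. Across 0.5 to 3 a day the range is 78% to 22% with random timing and 75% to none with even spacing. The expected consequence is lost precision in an exploratory outcome, with possible selection bias if bowel habit differs by group. It should be corrected, but it does not threaten the study as a whole.

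**What to change.** 1. Reconcile Section 4.6.20 with the exercise stress visit table in Section 25.1 by collecting all stool from Visit 2 admission to CPET.
2. Name the last stool before CPET as the pre-exercise baseline, and record its time before CPET.
3. Where a participant has two or more stools before CPET, report the drift from first to last as a check on the diet and admission effect.
4. State in Section 12.1 how a participant with no pre-exercise stool at Visit 2 is handled. If the Visit 1 stool is used, report that analysis separately.
5. Repeat the pre/post analysis restricted to baselines within 12 hours of CPET. Section 12.3 refers to ME/CFS and healthy volunteer cohorts completed as of October 2020, so some participants will already have been through Visit 2, presumably under the 12-hour text. The restricted analysis keeps one baseline definition across earlier and later participants.

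The cost is a short amendment and a few more stools handled by a process already in place. Some baselines will be one to two days older and closer to the habitual diet; items 2, 3 and 5 make that visible. The gain is confined to participants still to be admitted for Visit 2, because stool not collected before CPET cannot be recovered.
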